5.4.2 Discontinuation of Entire Study

AbbVie may terminate this study prematurely, either in its entirety or at any study site, for reasonable cause provided that written notice is submitted in advance of the intended termination. The Investigator may also terminate the study at his/her site for reasonable cause, after providing written notice to AbbVie in advance of the intended termination. Advance notice is not required by either party if the study is stopped due to safety concerns. AbbVie will terminate the trial prematurely if any new safety signal for the study drug is identified which indicates an unacceptable risk for patients in this trial. If AbbVie terminates the study for safety reasons, AbbVie will immediately notify the Investigator by telephone and subsequently provide written instructions for study termination.

5.5 Treatments

5.5.1 Treatments Administered

T2T Group

Treatment escalation steps are as follows:

- Basic Treatment (NSAID 1): Treatment will be started with any NSAID at full anti-inflammatory dose and given for 4 weeks (see Appendix Y). Early escape is possible, if after 2 weeks no ASAS 20 response is achieved. In this case, treatment can be switched to Escalation Step 1 at the Week 2 visit. If the chosen NSAID cannot be continued due to intolerance, escalation to the next

escalation step is possible at any time point. If Basic Treatment is well tolerated and ASDAS is < 2.1 the subject will be continued on this treatment.

- Escalation Step 1 (NSAID 2): At Week 4 (after 4 weeks of NSAID 1), if ASDAS is ≥ 2.1 or treatment with NSAID 1 is not tolerated, treatment will be changed to a second NSAID at full anti-inflammatory dose (see Appendix Y). The second NSAID will be given for 4 weeks. Early escape is possible if after 2 weeks (at Week 6 or Week 4 for subjects who early escaped from Basic Treatment) no ASAS 20 response is achieved. In this case, treatment can be switched to Escalation Step 2 after 2 weeks of NSAID 2. If the chosen NSAID cannot be continued due to intolerance, escalation to the next escalation step is possible at any time point. In that case, adalimumab may be combined the second or – if deemed required by the treating physician – the first NSAID used (provided escalation from Basic Treatment to Escalation Step 1 did not occur due to any safety issues related to NSAID 1 therapy). If NSAID 2 treatment is well tolerated and ASDAS is < 2.1 , the subject will be continued on this treatment.
- Escalation step 2 (Combination with adalimumab): In case of failure of NSAID 2 (ASDAS ≥ 2.1 after 4 weeks of NSAID 2) the treatment will be intensified by switching to the combination of NSAID and adalimumab 40 mg s.c. eow. Escalation step 2 can be initiated at Week 4 visit at the earliest if early escape is chosen during basic treatment and during NSAID 2.

Since subjects may be unfamiliar with sterile SC injection technique, qualified study site personnel will instruct them on proper technique and should directly observe the first injection of study drug to ensure proper injection technique (Appendix U). This supervision will serve as a confirmation of the use of safe and appropriate drug injection techniques and to answer any questions related to drug administration.

SOC Group

Subjects will receive treatment according to local SOC. For use of NSAID please see Appendix Y.

5.5.2 Identity of Investigational Product

The individual study drug information is presented in Table 3.

Table 3. Identity of Investigational Products

Drug	Dosage Form	Device	Formulation	Manufacturer
Adalimumab	Parenteral	Pre-filled syringe	40 mg/0.8 mL solution for injection Adalimumab/Mannitol, Citric acid monohydrate, Sodium citrate, Disodium phosphate dihydrate, Sodium dihydrogen phosphate dihydrate, Sodium chloride, Polysorbate 80, Water for injections, Sodium hydroxide added as necessary to adjust pH	AbbVie

5.5.2.1 Packaging and Labeling

Investigational product (IP) will be packaged separately in 0.8 mL syringes containing adalimumab 40 mg/0.8 mL. Each dosing kit carton will contain two pre-filled syringes to accommodate study design.

The syringe and/or carton labels will minimally contain the information as required per country requirements.

All labels must remain affixed to study medication at all times, and should never be removed for any reason.

5.5.2.2 Storage and Disposition of Study Drug

Adalimumab pre-filled syringes are to be stored protected from light at 2° to 8°C/36° to 46°F. Study medication drug **must not be frozen** at any time. A storage temperature log is to be maintained to document proper storage conditions. The refrigerator temperature must be recorded on each business day. Malfunctions or any temperature excursion must be reported to the Sponsor immediately. Study medication should be quarantined and not dispensed until AbbVie Global Pharmaceutical Research and Development (GPRD) or

AbbVie Temperature Excursion Management System (ATEMS) deems the medication as acceptable.

All clinical supplies must be stored and locked in a secure place until they are dispensed for subject use or are destroyed via on-site destruction (if allowed by AbbVie, local guidelines and a well-documented procedure is in place) or returned to AbbVie.

Investigational products are for investigational use only and are to be used only within the context of this study.

5.5.3 Method of Assigning Subjects to Treatment Groups

All subjects will be enrolled at the Baseline Visit and centrally randomized in a 1:1 ratio to the two treatment arms (intensified T2T or SOC). Centralized permuted block randomization will be performed.

5.5.4 Selection and Timing of Dose for Each Subject

Subjects should take study medication as outlined in Section 5.5.1.

If a subject should in the T2T group forget to administer the injection of study medication on their regularly scheduled dosing date, they should take the forgotten injection as soon as they remember the dose was missed up to the day of their next scheduled dose. The subject should not administer two doses on the same day.

In the event the incorrect dose is taken or a dose is missed, the subject should be instructed to contact the site to determine how to proceed with dosing. The subject must record all dosing information on the Subject-Dosing Diary Sheet (Appendix V).

Doses not administered (e.g., not taken before next dose is scheduled), should be recorded as not taken in the source. Remaining doses should be fully returned to the study site. The subject should resume their regular dosing schedule based on the first dosing date at Baseline.

5.5.5 Blinding**5.5.5.1 Blinding of Investigational Product**

Neither the investigator(s) nor their study staff, or subjects will be blind to the treatment arm subjects are randomized to. The investigator should not influence their SOC treatment based upon knowledge and potential benefits/risks in the intensified T2T treatment arm.

5.5.6 Treatment Compliance

The Investigator or his/her designated representatives will dispense study drug only for use by subjects enrolled in the study.

The subject or their qualified designee will administer all doses of study drug. Appropriate site staff will supervise the first administration of the study drug in-office to ensure proper injection technique. In order to document compliance with the treatment regimen, the subject will be given a subject dosing diary sheet (Appendix V) to record all injection dates and times. Compliance information will be documented on the appropriate eCRF. Subjects will be counseled on missed doses of medication. Subjects will be instructed to return all drug containers (even if empty) to the study site. If the subject does not return the subject dosing diary sheet, IP boxes and sharp containers (when applicable), the site should question the subject and obtain as much information as possible as to the dosing of the study drug. The information should be documented on the source documents as per "best recollection" and when possible re-verified once the dosing sheet is returned before completing the applicable eCRF page.

5.5.7 Drug Accountability

The Investigator or designee will verify that study drug supplies are received intact, at the appropriate temperature, and in the correct amounts. This will be accomplished by documenting the condition of the shipment, verifying the kit numbers in the package against the Proof of Receipt (POR) or similar document included with each drug shipment, and documenting this verification by signing and dating the POR or similar

document. The original POR Note or similar document will be kept in the site files as a record of what was received.

In addition, an accurate running inventory of study drug will be kept by the site on a Site Drug Accountability log including date received, the lot number, kit number(s), date dispensed, subject number, and the identification with date of the person dispensing the drug.

All empty IP boxes and used pre-filled syringes will be inventoried by the site. Each subject will be given their own sharps disposal container to store used pre-filled syringes. Empty IP boxes and Sharps containers should be returned by the subject at each visit for accountability and compliance purposes and new containers issued as necessary. Empty Boxes and returned Sharps containers will be retained (unless prohibited by local law) until the CRA is on site to confirm the returned medication. CRAs and site staff will complete study medication accountability via study medication logs, source documents, subject dosing sheets, empty IP boxes and by visually inspecting the syringes in the Sharps container whenever possible. Used Sharps containers should never be opened. Once the CRA has verified drug accountability at the site, the site staff may destroy or initiate shipment for shipment of used pre-filled syringes. Site staff and CRA will document that the used pre-filled syringes have been destroyed, using appropriate biohazard precautions, when appropriate. A copy of the destruction methodology should be maintained at the site's facility. At the end of the study, after drug accountability has been completed at the site and verified by the CRA, unused medication will be returned to a destruction facility by the CRA or – if approved by AbbVie and permitted according to local guidelines – destroyed at site (or by a third party vendor contracted by the site).

5.6 Discussion and Justification of Study Design

5.6.1 Discussion of Study Design and Choice of Control Groups

This clinical trial was designed to compare a T2T intensified treatment approach (escalating quickly with two different NSAIDs to a combination of adalimumab with NSAID) with SOC in reducing disease activity/achieving remission in patients with

axSpA. Recently T2T recommendations for the whole group of SpA including patients with axSpA have been developed. However, a T2T approach starting with NSAID treatment and escalating to combining NSAID with a TNF blocker has not yet been investigated.

The duration of 52 weeks was chosen to reasonably reflect long term treatment of chronic disease.

5.6.2 Appropriateness of Measurements

Standard statistical, clinical and laboratory procedures will be utilized in this study. Efficacy measurements in this study have been selected to assess disease activity in subjects with axSpA. Other than the biomarker analysis and the measurement of MRI progression which will be exploratory, all clinical and laboratory procedures in this study are standard and generally accepted.

5.6.3 Suitability of Subject Population

Males and females at least 18 years of age with axSpA who have a minimum level of disease activity at Baseline (ASDAS ≥ 2.1). Confining the duration of disease to < 5 years and including only subjects who are TNF-alpha-blocker-naïve and either NSAIDs-naïve or should not have taken NSAIDs at maximal recommended dose over the last 2 weeks prior to Baseline minimizes the probability to include treatment experienced/resistant subjects.

5.6.4 Selection of Doses in the Study

The recommended dose of adalimumab for adults with AS and nr-axSpA is 40 mg administered eow. Adalimumab is approved for the treatment of AS and nr-axSpA in the EU. Adalimumab was generally well-tolerated and has demonstrated therapeutic efficacy compared to placebo in AS subjects in Study M03-607 (ATLAS) and Study M03-606 as well as in nr-axSpA subjects in Study M10-791 which were the pivotal studies used to support registration for these indications.

6.0 Complaints

A Complaint is any written, electronic, or oral communication that alleges deficiencies related to the physical characteristics, identity, quality, purity, potency, durability, reliability, safety, effectiveness, or performance of a product/device after it is released for distribution

The study medication in this trial contains both:

A Biologic compound and

Device components (pre-filled syringe)

Complaints associated with any component of this study medication must be reported to the Sponsor (Section 6.2.2). For adverse events, please refer to Sections 6.1 through 6.1.6. For product complaints, please refer to Section 6.2.

6.1 Medical Complaints

The Investigator will monitor each subject for clinical and laboratory evidence of adverse events on a routine basis throughout the study. The Investigator will assess and record any adverse event in detail including the date of onset, event diagnosis (if known) or sign/symptom, severity, time course (end date, ongoing, intermittent), relationship of the adverse event to Humira, and any action(s) taken. For serious adverse events considered as having "no reasonable possibility" of being associated with Humira, the Investigator will provide an "Other" cause of the event. For adverse events to be considered intermittent, the events must be of similar nature and severity. Adverse events, whether in response to a query, observed by site personnel, or reported spontaneously by the subject will be recorded.

All adverse events will be followed to a satisfactory conclusion.

6.1.1 Definition**6.1.1.1 Adverse Event**

An AE is defined as any untoward medical occurrence in a subject or clinical investigation subject administered a pharmaceutical product and which does not necessarily have a causal relationship with this treatment. An adverse event can therefore be any unfavorable and unintended sign (including an abnormal laboratory finding), symptom, or disease temporally associated with the use of a medicinal (investigational) product, whether or not the event is considered causally related to the use of the product.

Such an event can result from use of the drug as stipulated in the protocol or labeling, as well as from accidental or intentional overdose, drug abuse, or drug withdrawal. Any worsening of a pre-existing condition or illness is considered an adverse event.

Worsening of SpA per investigator judgment is considered an AE, however the expected manifestations of disease (arthritis, enthesitis, back pain, etc.) are not considered AEs. Worsening in severity of a reported adverse event should be reported as a new adverse event. Laboratory abnormalities and changes in vital signs are considered to be adverse events only if they result in discontinuation from the study, necessitate therapeutic medical intervention, (meets protocol specific criteria [see Section 6.1.7 regarding toxicity management]) and/or if the Investigator considers them to be adverse events.

An elective surgery/procedure scheduled to occur during a study will not be considered an adverse event if the surgery/procedure is being performed for a pre-existing condition and the surgery/procedure has been pre-planned prior to study entry. However, if the pre-existing condition deteriorates unexpectedly during the study (e.g., surgery performed earlier than planned), then the deterioration of the condition for which the elective surgery/procedure is being done will be considered an adverse event.

6.1.1.2 Serious Adverse Events

If an adverse event meets any of the following criteria, it is to be reported to AbbVie as a serious adverse event (SAE) within 24 hours of the site being made aware of the serious adverse event.

Death of Subject	An event that results in the death of a subject.
Life-Threatening	An event that, in the opinion of the Investigator, would have resulted in immediate fatality if medical intervention had not been taken. This does not include an event that would have been fatal if it had occurred in a more severe form.
Hospitalization or Prolongation of Hospitalization	An event that results in an admission to the hospital for any length of time or prolongs the subject's hospital stay. This does not include an emergency room visit or admission to an outpatient facility.
Congenital Anomaly	An anomaly detected at or after birth, or any anomaly that results in fetal loss.
Persistent or Significant Disability/Incapacity	An event that results in a condition that substantially interferes with the activities of daily living of a study subject. Disability is not intended to include experiences of relatively minor medical significance such as headache, nausea, vomiting, diarrhea, influenza, and accidental trauma (e.g., sprained ankle).
Important Medical Event Requiring Medical or Surgical Intervention to Prevent Serious Outcome	An important medical event that may not be immediately life-threatening or result in death or hospitalization, but based on medical judgment may jeopardize the subject and may require medical or surgical intervention to prevent any of the outcomes listed above (i.e., death of subject, life-threatening, hospitalization, prolongation of hospitalization, congenital anomaly, or persistent or significant disability/incapacity). Additionally, any elective or spontaneous abortion or stillbirth is considered an important medical event. Examples of such events include allergic bronchospasm requiring intensive treatment in an emergency room or at home, blood dyscrasias or convulsions that do not result in inpatient hospitalization, or the development of drug dependency or drug abuse.

For serious adverse events with the outcome of death, the date and cause of death will be recorded on the appropriate case report form.

6.1.2 Adverse Event Severity

The Investigator will use the following definitions to rate the severity of each adverse event:

Mild	The adverse event is transient and easily tolerated by the subject.
Moderate	The adverse event causes the subject discomfort and interrupts the subject's usual activities.
Severe	The adverse event causes considerable interference with the subject's usual activities and may be incapacitating or life-threatening.

6.1.3 Relationship to Humira

The Investigator will use the following definitions to assess the relationship of the adverse event to the use of Humira:

Reasonable Possibility	After consideration of factors including timing of the event, biologic plausibility, clinical judgment, and potential alternative causes, there is sufficient evidence (information) to suggest a causal relationship.
No Reasonable Possibility	After consideration of factors including timing of the event, biologic plausibility, clinical judgment, and potential alternative causes, there is insufficient evidence (information) to suggest a causal relationship.

For causality assessments, events assessed as having a reasonable possibility of being related to Humira will be considered "associated." Events assessed as having no reasonable possibility of being related to Humira will be considered "not associated." In addition, when the Investigator has not reported a causality or deemed it not assessable, AbbVie will consider the event associated.

[figure not shown]
If an Investigator's opinion of no reasonable possibility of being related to Humira is given, an "Other" cause of event must be provided by the Investigator for the adverse event.

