1. Subjects must have signed written informed consent before starting any study-related assessments or procedures.
2. Diagnosis of axSpA (either ankylosing spondylitis or non-radiographic axSpA) and fulfilling the ASAS classification criteria for axSpA.
3. Subjects aged ≥ 18 years.
4. Disease duration < 5 years.
5. Subjects must have a baseline disease activity as defined by having an ASDAS ≥ 2.1 or a BASDAI ≥ 4 .
6. Subjects must be either NSAID-naïve or had not been treated with the maximal recommended dose during the last 2 weeks prior to the Baseline Visit.
7. Subjects must never have failed a NSAID taken at maximal recommended dose for 2 weeks or more.

Main Exclusion:

1. Contraindications for NSAIDs or Tumor Necrosis Factor (TNF) blocker according to local labeling.
2. If entering the study on concomitant NSAIDs, subjects taking the maximal recommended dose during the last 2 weeks prior to the Baseline Visit or have failed or developed intolerance to a NSAID taken at maximal recommended dose for 2 weeks or more at any time.

Diagnosis and Main Criteria for Inclusion/Exclusion (Continued):**Main Exclusion (Continued):**

3. Prior exposure to any anti-TNF therapy; any biologic therapy with a potential therapeutic impact on SpA, or subject has been treated with any investigational drug of chemical or biologic nature within a minimum of 30 days or five half-lives (whichever is longer) of the drug prior to the Baseline Visit.

Investigational Product: Adalimumab

Dose: 40 mg eow

Mode of Administration: s.c.

Reference Therapy: Local Standard of Care

Duration of Treatment:

Subjects will be treated for 52 weeks receiving either treatment according to the T2T intensified treatment scheme or SOC. Study drug will only be administered in the T2T group. Length of exposure will depend on individual necessity for intensifying treatment. The maximal duration of treatment with adalimumab is up to 48 weeks.

Criteria for Evaluation:**Efficacy:**

The primary efficacy endpoint is the clinical disease activity at Week 32 as measured by the percentage of subjects in ASDAS inactive disease (ASDAS < 1.3).

Secondary efficacy endpoints include the following at Week 32 and Week 52:

- Quality of life by the European Quality of Life – 5 Dimension Questionnaire (EQ-5D)
- Work Productivity and Activity Impairment – axSpA (WPAI-axSpA)
- Overall functioning by ASAS HI
- Disease activity as measured by BASDAI

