8.1.6 Safety Analysis

Safety analyses will be carried out using the safety population, which include all subjects who were randomized and received treatment for axSpA after randomization.

Treatment-emergent AEs and serious AEs (SAEs), which include pre- and post-treatment SAEs, will be summarized and reported, while pre-randomization AEs will be only listed.

Treatment-emergent AEs are defined as AEs that begin either on or after the Baseline Visit up to end of the study. All AEs will be coded using the Medical Dictionary for Drug Regulatory Activities (MedDRA®). The number and percent of subjects experiencing treatment emergent AEs will be tabulated by system organ class and preferred term. In addition, a summary of treatment emergent AEs by severity and relationship to study drug will be presented. AEs, which are serious, severe, or life-threatening, and those which lead to premature study discontinuation will be listed and described in detail.

Mean change in vital signs and laboratory variables at each visit as compared to Baseline will be summarized for all subjects in the safety population, and compared between treatment groups using a one way ANOVA. The last evaluation on or before the Baseline Visit will be used as baseline for all analyses. For selected parameters, a listing of all subjects with any laboratory determination meeting Common Toxicity Criteria (CTC) of Grade 3 or higher will be provided. Shift tables for changes from Baseline according to the normal range will also be provided for laboratory variables.

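### The rule that unreported or non-assessable causality counts as Humira-associated has no exposure condition, so it can label events in subjects who had not received Humira (minor)

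*Protocol*

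**What the plan says.** Section 6.1 covers all subjects: "The Investigator will monitor each subject for clinical and laboratory evidence of adverse events on a routine basis throughout the study". For any adverse event, the items to be recorded include the "relationship of the adverse event to Humira, and any action(s) taken".

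Section 6.1.3 gives two categories, reasonable possibility and no reasonable possibility, both defined as relationship to Humira. It has no category for subjects who have not received the drug. It then adds the default: "In addition, when the Investigator has not reported a causality or deemed it not assessable, AbbVie will consider the event associated".

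Exposure to study drug is partial by design. The Synopsis states: "Study drug will only be administered in the T2T group". Of exposure within that arm it says: "Length of exposure will depend on individual necessity for intensifying treatment". Under Sections 5.1 and 5.5.1, T2T subjects start on an NSAID, remain on it if it works and is tolerated, and receive adalimumab only at Escalation Step 2.

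Section 8.1.1 defines the safety population as everyone randomized who received any treatment for axial spondyloarthritis. Section 8.1.6 starts the treatment-emergent period at the Baseline Visit and promises that "a summary of treatment emergent AEs by severity and relationship to study drug will be presented".

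**The concern.** Counting missing causality as related is a sensible cautious convention where the subject has had the drug. Where the subject has not, the label is simply false: an event cannot be associated with a product never received, or not yet received.

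In this trial such events are common by design. They are not confined to a few protocol deviations, because one arm is not given study drug and the other receives it late or not at all. The default is written without regard to this.

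The summary by relationship is the table a reader would use to attribute harm to adalimumab within the strategy. Any event mislabelled in this way would appear there as drug-related with no exposure behind it.

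**Working it through.** The plan states no figure on this point, so there is nothing to reproduce. The check is to trace the default through the text and look for an exposure condition at each step.

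1. **Who gets a causality entry?** Section 6.1: every subject, any adverse event. No limit by arm or first dose.
2. **What does the entry refer to?** Section 6.1.3: Humira, not the assigned strategy or an NSAID.
3. **What happens to a blank or not-assessable entry?** Section 6.1.3: associated. No limit by arm or first dose.
4. **Who is in the analysis set?** Section 8.1.1: all randomized subjects treated for the disease, so SOC and NSAID-only T2T subjects are included.
5. **Which events count?** Section 8.1.6: those from the Baseline Visit onward, not from first adalimumab dose. On the early-escape path, Sections 5.1 and 5.5.1 put the start of adalimumab at Week 4 at the earliest, so T2T events before that point are included without exposure.
6. **Is the table restricted?** Section 8.1.6: no exposure restriction is stated.

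No step exempts unexposed events. Three groups are caught: SOC subjects not given Humira, T2T subjects who stay on NSAIDs, and T2T events before the first adalimumab dose.

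**Illustration of size.** Let *n* be the number of adverse events without prior Humira exposure and *m* the share with causality blank or not assessable. Then:

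- expected number mislabelled = *n* × *m*
- chance of at least one = 1 − (1 − *m*)^*n*, treating entries as independent

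The protocol gives neither *n* nor *m*. I assume *n* = 100, or *n* = 249 (the standard-care adverse event count that Section 3.8 quotes from a psoriatic arthritis trial), and *m* from 0% to 5%.

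| *n* (assumed) | *m* (assumed) | Expected mislabelled | Chance of at least one |
|---|---|---|---|
| 100 | 0% | 0 | 0% |
| 100 | 1% | 1.0 | 63% |
| 100 | 5% | 5.0 | 99% |
| 249 | 0% | 0 | 0% |
| 249 | 1% | 2.5 | 92% |
| 249 | 5% | 12.5 | >99% |

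For example, 249 × 0.01 = 2.49 and 1 − 0.99^249 = 0.918. The range starts at zero because nothing in the protocol rules zero out.

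**The case against.** The best defence is that the rule, followed properly, gives the right answer. Section 6.1 makes the causality entry part of every adverse event record. The criteria in 6.1.3 include timing and biologic plausibility, and for someone never given Humira these lead to no reasonable possibility, hence not associated. A wrong label needs a site to leave the item blank or call it not assessable, and that entry to survive review. Section 10.2 provides for periodic review of eCRFs for completeness and investigator sign-off. Section 11.0 adds logic checks, manual checks and source review. All of this stands, and it means that how often the default is triggered is an open question. The checks bear mainly on blanks; a completed not-assessable entry could pass them.

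A reader might infer that a blank is the usual entry for an unexposed subject. The protocol does not support that, for the reasons just given. It is true that 6.1.3 has no not-applicable option and requires an alternative cause when no reasonable possibility is chosen, but this does not show that sites would leave the item empty.

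Three further points are fair:

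- Section 5.2.3.3 prohibits no medication in the SOC arm, so some SOC subjects may receive commercial Humira. Asking about Humira in both arms therefore has a purpose, and the SOC arm cannot be treated as wholly unexposed.
- Section 6.1.3 speaks of Humira and Section 8.1.6 of study drug. That the table uses the 6.1.3 classification, default included, is the natural reading but is not stated.
- Section 8.1.2 leaves full analysis details to the SAP, which could restrict the table. It would still start from a classification rule that the protocol itself fixes without an exposure condition.

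**Conclusion.** The point holds as a minor defect of wording. The default in 6.1.3 gives a false label whenever it is triggered for an event without prior exposure, and no section exempts such events. The frequency is unknown and may be zero. That it reaches the table rests on reading 8.1.6 as using the 6.1.3 classification.

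Two stronger conclusions should not be drawn. A reader might infer that the relationship summary becomes uninterpretable, or that the adalimumab-related rate in T2T is distorted. The documents do not support this: nothing shows how many entries would be affected, and unexposed status can be identified from the dosing and medication records. A reader might also take 249 events and a missing share of 2% to 5% and expect about 5 to 12 mislabelled SOC events (249 × 0.02 = 4.98; 249 × 0.05 = 12.45). That share has no source in the protocol, the count comes from a trial in another disease, and the sum treats every SOC event as unexposed.

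The effect is limited to the summary by relationship. The primary endpoint and overall adverse event incidence do not use causality, and Section 6.1.5 requires serious events to be reported whether or not they are related to Humira.

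**What to change.** - **Section 6.1.3:** apply the default for unreported or non-assessable causality only to adverse events with onset on or after the subject's first dose of adalimumab from any source. Code all other adverse events as not applicable, not exposed. Wording it as any source keeps the cautious default for SOC subjects who receive commercial Humira.
- **Section 8.1.6:** present the summary by relationship for adalimumab-exposed subjects, counting events from first dose.

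The cost is one sentence in each section and one additional eCRF code. No new data are needed: T2T dosing is already documented (5.5.6), and SOC treatment for the disease is already recorded (5.2.3.2), with start and end dates under 5.2.3.
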